### **3.2.2 Objective response rate**

ORR (per RECIST 1.1 using investigator assessments) is defined as the number (%) of patients with at least 1 visit response of CR or PR. Data obtained up until progression, or the last evaluable assessment in the absence of progression, will be included in the assessment of ORR. Patients who discontinue study treatment without progression, receive a subsequent therapy, and then respond will not be included as responders in the ORR.

Patients who continue study treatment through progression and subsequently respond with further treatment would not be included as responders in ORR assessment. Likewise, patients on the MEDI4736 + tremelimumab combination therapy arm who progress during the monotherapy portion of the regimen and subsequently respond with the optional retreatment regimen would not be included as responders in the ORR assessment.

### **3.2.3 Duration of response**

DoR (per RECIST 1.1 as assessed by investigator) will be defined as the time from the date of first documented response until the first date of documented progression or death in the absence of disease progression (i.e., date of PFS event or censoring – date of first response + 1). The end of response should coincide with the date of progression or death from any cause used for the RECIST 1.1 PFS endpoint.

The time of the initial response will be defined as the latest of the dates contributing towards the first visit response of CR or PR. If a patient does not progress following a response, then their DoR will be censored at the PFS censoring time. DoR will not be defined for those patients who do not have documented response.

### **3.2.4 Time to response**

Time to response (per RECIST 1.1 as assessed by the investigator) is defined as the time from the date of randomization until the date of documented response. The date of documented response should coincide with that used for the RECIST 1.1 DoR endpoint.

### **3.2.5 Proportion of patients alive and progression free at 6 and 12 months**

The APF6 and APF12 will be defined as the Kaplan-Meier estimate of PFS (per RECIST 1.1 as assessed by investigator) at 6 months and 12 months respectively.

### **3.2.6 Proportion of patients alive at 12, 18 and 24 months**

The OS12, OS18 and OS24 will be defined as the Kaplan-Meier estimate of OS at 12, 18 and 24 months respectively after randomization.

### **3.2.7 Time from randomization to the first subsequent therapy or death (TFST)**

Time to the first subsequent therapy (TFST) or death will be defined as the time from the date of randomization to the earlier of either the start date of the first subsequent anticancer therapy after discontinuation of randomized treatment or the date of death (i.e., the date of first subsequent cancer therapy, death, or censoring defined as the date of randomization + 1 day). Any patient not known to have received a first subsequent anticancer therapy will be censored at the last date that the patient was known not to have received a first subsequent anticancer therapy. If a patient terminated the study before the first subsequent therapy for a reason other than death, the patient will be censored at the earliest of either the patient's last known date to be alive or the study termination date.

### **3.2.8 Time from randomization to second subsequent therapy or death (TSST)**

As a supportive summary to PFS2, time to second subsequent therapy (TSST) or death will be defined as the time from the date of randomization to the earlier of either the start date of the second subsequent anticancer therapy after discontinuation of first subsequent therapy, or the date of death. Any patient not known to have had a second subsequent anticancer therapy will be censored at the last date when the patient was known not to have received a second subsequent anticancer therapy. If a patient terminated the study for reason other than death before second subsequent anticancer therapy, the patient will be censored at the earliest of the last known to be alive and termination dates.

### **3.2.9 Time from randomization to second progression-free survival (PFS2)**

PFS2 will be defined as the time from the date of randomization to the earliest of the progression event subsequent to first subsequent therapy (TFST) or death. Note the patient does not need to remain on their second treatment for the progression event to occur. The date of second progression will be recorded by the Investigator in the eCRF (PFS2 CRF) and defined according to local standard clinical practice and may involve any of the following: objective radiological imaging, symptomatic progression, or death. Second progression status will be reviewed (every 6 weeks for the first 24 weeks relative to the date of randomization and then every 8 weeks thereafter) following the progression event used for the primary

variable PFS (the first progression) and status recorded. Patients alive and for whom a second disease progression has not been observed should be censored at the later of the date of assessment on the PFS2 form indicating no progression (PFSRESP=2) or at the date of the last evaluable RECIST assessment (or day 1 if no post-baseline RECIST data is available; date of withdrawal, date last known alive, DCO or, if a patient has not had a first subsequent therapy; the date last known not to have received a first subsequent therapy (TFST censoring date).

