ORR (per RECIST 1.1 using investigator assessments) is defined as the number (%) of patients with at least 1 visit response of CR or PR. Data obtained up until progression, or the last evaluable assessment in the absence of progression, will be included in the

assessment of ORR. Patients who go off treatment without progression, receive a subsequent therapy, and then respond will not be included as responders in the ORR.

Duration of response

DoR (per RECIST 1.1 using investigator assessments) will be defined as the time from the date of first documented response until the first date of documented progression or death in the absence of disease progression (ie, date of PFS event or censoring – date of first response + 1). The end of response should coincide with the date of progression or death from any cause used for the RECIST 1.1 PFS endpoint.

The time of the initial response will be defined as the latest of the dates contributing toward the first visit response of CR or PR. If a patient does not progress following a response, then their DoR will be censored at the PFS censoring time. DoR will not be defined for those patients who do not have documented response.

Time from randomization to second progression (PFS2)

PFS2 will be defined as the time from the date of randomization to the earliest of the progression event subsequent to that used for the PFS endpoint or death. The date of second progression will be recorded by the Investigator in the eCRF and defined according to local standard clinical practice and may involve any of the following: objective radiological imaging, symptomatic progression, or death. Second progression status will be reviewed (every 6 weeks for the first 48 weeks relative to the date of randomization and then every 8 weeks thereafter) following the progression event used for the primary variable PFS (the first progression) and status recorded. Patients alive and for whom a second disease progression has not been observed should be censored at the last time known to be alive and without a second disease progression, that is, censored at the latest of the PFS or PFS2 assessment date if the patient has not had a second progression or death.

Time from randomization to the first subsequent therapy or death

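### The SAP's PFS2 censoring sentence is malformed and departs from the protocol; on one literal reading it carries patients lost early to the data cut-off as free of second progression

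*SAP*

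**What the plan says.** The rule in SAP 3.2.9 is a single sentence. Its population is stated: "Patients alive and for whom a second disease progression has not been observed should be censored". Its operator and first date follow: such patients "should be censored at the later of the date of assessment on the PFS2 form indicating no progression". The second date is "or at the date of the last evaluable RECIST assessment (or day 1 if no post-baseline RECIST data is available". The bracket opened there never closes. After a semicolon the sentence goes on: "date of withdrawal, date last known alive, DCO or, if a patient has not had a first subsequent therapy", and ends with the TFST censoring date.

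Protocol 8.4.1.3 covers the same patients. They are "censored at the last time known to be alive and without a second disease progression", which it then spells out as "censored at the latest of the PFS or PFS2 assessment date if the patient has not had a second progression or death". DCO, withdrawal, date last known alive and the TFST censoring date do not appear in it.

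The neighbouring SAP rule for TSST (3.2.8) names its operator for patients who leave the study: "the patient will be censored at the earliest of the last known to be alive and termination dates". TFST (3.2.7) does the same.

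PFS2 is analysed by stratified log-rank test with HR, CI and p-value (SAP 4.2.8). SAP 4.1 limits formal analysis to OS and gives nominal p-values elsewhere.

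**The concern.** The sentence has one operator, *the later of*, and six candidate dates. A programmer who applies that operator to all six gets the DCO whenever the data have been cut at the DCO, because no other date can exceed it. A patient whose last clean assessment was in month 3 would then stay in the PFS2 risk set for years.

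Removing DCO alone would not cure this, because date last known alive is also in the list. Protocol 5.1.2 allows survival status to come from a telephone call to the patient, the family or a physician. Such contact shows that the patient is alive, not that there has been no second progression. After confirmed progression, scans follow local practice and are optional (Protocol Table 4), so survival contact can outlast any PFS2 assessment.

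At stake is a named secondary endpoint whose censoring dates could differ by years between two programmers working from the same text.

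**Working it through.** The documents state no sample size, event count or power for PFS2, so there is no plan figure to reproduce. The check parses the sentence and applies each reading to one patient. A rough size follows under assumed inputs.

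**Readings of the trailing dates**

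| Reading | What it needs | Result |
|---|---|---|
| (a) further members of the *later of* set | the only operator present, stretched past the two dates it grammatically takes | DCO for all patients covered |
| (b) fallbacks when there is no post-baseline RECIST date | an order of precedence, which is absent; the same bracket already gives Day 1 as the fallback | undefined |
| (c) caps | an *earliest of*, which is absent | assessment date, capped |

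**One patient (assumed dates, months from randomization).** PFS2 form at 2, last evaluable RECIST at 3, withdrawn and last known alive at 4. The timeline is from SAP 1.3: 17 months' accrual plus 23.6 months' minimum follow-up gives 40.6 months. The DCO therefore falls 23.6 to 40.6 months after randomization, depending on entry date.

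- Later of the two assessment dates (close to the protocol rule): max(2, 3) = month 3.
- Earliest of withdrawal, last known alive and DCO: month 4.
- Later of the whole list: month 23.6 to 40.6.
- Unobserved event-free time under (a), against month 3: 23.6 − 3 = 20.6 to 40.6 − 3 = 37.6 months.
- OS for this patient is censored at the last date known alive (SAP 3.2.1), month 4. Under (a), PFS2 time would exceed known survival time.

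**Illustrative size under (a).** Assumptions: exponential PFS2 with median 8 months; a fraction p lost, uniformly over months 0–12; no later deaths captured among those lost. The small effect of DCOs between 23.6 and 24 months is ignored.

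- True 24-month PFS2: 0.5^(24/8) = 0.125.
- Mean probability of being event-free at loss: (1/12)∫₀¹² 0.5^(t/8) dt = [8/(12 ln 2)] × (1 − 0.5^1.5) = 0.962 × 0.646 = 0.622.
- Apparent 24-month PFS2: (1 − p) × 0.125 + p × 0.622.

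| p | Apparent 24-month PFS2 |
|---|---|
| 3% | 0.121 + 0.019 = 14.0% |
| 5% | 0.119 + 0.031 = 15.0% |
| 10% | 0.1125 + 0.0622 = 17.5% |

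Simulation with 400,000 patients per scenario gave 14.1%, 15.1% and 17.5%. A smaller one (20,000 patients) gave 14.6% and 17.9% at 5% and 10% loss. In the smaller run, 5% loss moved the median from 8.0 to about 8.2 months, and censoring at the loss date instead returned 12–13% and a median of 8.0. With an assumed median of 9 months, 5% loss moves the 24-month figure from 15.7% to 18.2%.

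These are single-curve results. No between-arm scenario or HR was computed.

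**The case against.** A reader might infer that the SAP definitely censors every patient without a PFS2 event at the DCO. The documents do not support that.

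- *Grammar.* *Later of* compares two things, and two assessment dates are supplied. The trailing dates come after a semicolon inside an unclosed bracket, and the TFST date is conditional on no first subsequent therapy.
- *Redundancy.* If the rule always returned DCO, naming the other dates would be pointless, which counts against that intent.
- *Context.* TFST and TSST use *earliest of*. Survival calls are made after the DCO (SAP 3.2.1), so a raw last-alive date can fall later than the DCO, and listing the DCO makes sense as a limit.
- *Scope.* The rule covers patients who are alive, since death is a PFS2 event. Survival follow-up continues after withdrawal of consent unless expressly refused (Protocol 3.10.2), and status is re-checked through records and registries (3.10.3). Many patients who stop PFS2 assessments would still contribute a death.

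All of this stands against treating the always-DCO result as the rule. It does not rescue the sentence. The cap reading needs an operator that the two preceding sections state and this one omits. The fallback reading collides with the Day 1 fallback in the same bracket. Neither is a complete instruction as printed.

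**Conclusion.** The PFS2 censoring rule in SAP 3.2.9 cannot be programmed as written and does not match Protocol 8.4.1.3. Carrying patients to the DCO is one literal reading, not the established rule, and applies only to patients alive without an observed second progression. On that reading, those also lost to survival follow-up are counted as event-free beyond their own OS censoring date.

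The size is illustrative: about 15% against 12.5% at 24 months with 5% loss. It rests on an assumed median, loss rate and loss timing, and on no later deaths being captured; captured deaths would shrink it. A reader might also infer a biased HR or log-rank test. What happens to the HR depends on how loss differs between arms; nothing in the documents gives that, and it was not computed.

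PFS2 is outside the multiple testing procedure and primary OS is untouched. The entry in the SAP table of changes from the protocol is redacted, so whether this difference was declared cannot be judged. The sentence should be corrected before the derivation is programmed.

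**What to change.** Replace the sentence with one explicit rule aligned with Protocol 8.4.1.3:

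- Patients alive without an observed second progression are censored at the latest PFS (RECIST) or PFS2 assessment documenting no second progression, or at Day 1 if there is none.
- The censoring date is never later than the earliest of withdrawal, date last known alive and DCO.

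Censoring patients with no first subsequent therapy at the TFST censoring date is not in the protocol rule, because that date need not be an assessment date. If it is kept, state it as a separate conditional rule with the same caps and declare it as a change from the protocol.

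Cost: SAP wording and one derivation. No new data are needed.

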### **3.2.10 Change in tumor size**

For supportive purposes percentage change from baseline in tumor size will be derived at each scheduled tumor assessment visit (hereafter referred to as week X for convenience). Best percentage change from baseline in tumor size will also be derived as the biggest decrease or, if no decrease, as the smallest increase in tumor size from baseline.

This is based on RECIST1.1 target lesion measurements taken at baseline and at the timepoint of interest. Tumor size is defined as the sum of the longest diameters of the target lesions for the site investigator data based upon RECIST assessments. Target lesions are measurable tumor lesions. The change in target lesion tumor size at week X will be obtained for each patient by taking the difference between the sum of the target lesions at week X and the sum of the target lesions at baseline. To obtain the percentage change in target lesion tumor size at week X the change in target lesion tumor size is divided by the sum of the target lesions at baseline and multiplied by 100 (i.e.  $(\text{week X} - \text{baseline}) / \text{baseline} * 100$ ). More details on target lesions and measurements can be found in Section 3.1.

### **3.2.11 Best objective response (BoR)**

Best objective response (BoR) is calculated based on the overall visit responses from each RECIST 1.1 assessment, as described in Appendix F. It is the best response a patient has had during their time in the study up until RECIST 1.1 progression or the last evaluable assessment in the absence of RECIST 1.1 progression.

Categorization of BoR will be based on RECIST 1.1 (Appendix F) using the following response categories: CR, PR, SD, PD, and NE.

BoR will be determined programmatically based on RECIST 1.1 using all site investigator assessments up until the first progression event. For patients whose progression event is death, BoR will be calculated based upon all evaluable RECIST 1.1 assessments prior to death.

For determination of a best response of CR/PR, at least one determination of CR/PR must be observed before progression disease (PD)

For determination of a best response of SD, at least one SD should be recorded at 5 weeks (i.e., 6 weeks minus 1 week), i.e. at least 35 days (to allow for an early assessment within the assessment window), after date of randomization (and not qualifying for CR or PR).

For PD, patients who die with no evaluable RECIST 1.1 assessments, if the death occurs  $\leq 98$  days (i.e.,  $2 \times (6 \text{ weeks} \pm 1 \text{ week})$ ) after randomization, then BoR will be assigned to the progression (PD) category. For patients who die with no evaluable RECIST 1.1 assessments, if the death occurs  $> 98$  days (i.e.,  $2 \times (6 \text{ weeks} \pm 7 \text{ days})$ ) after the date of randomization, then BoR will be assigned to the NE category.

Progression events that have been censored due to them being  $> 90$  days because of 2 or more consecutive missed visits will not contribute to the BoR derivation.

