
BoR will be determined programmatically based on RECIST 1.1 using all investigator assessments up until the first progression event. For patients whose progression event is death, BoR will be calculated based upon all evaluable RECIST 1.1 assessments prior to death.

For patients who die with no evaluable RECIST 1.1 assessments, if the death occurs ≤ 90 days (ie, $2 \times (6 \text{ weeks} \pm 3 \text{ days})$) after randomization, then BoR will be assigned to the progression (PD) category. For patients who die with no evaluable RECIST 1.1 assessments, if the death occurs >90 days (ie, $2 \times (6 \text{ weeks} \pm 3 \text{ days})$) after the date of randomization, then BoR will be assigned to the NE category.

Progression events that have been censored due to them being >90 days after the last evaluable assessment will not contribute to the BoR derivation.

Time to response

Time to response (per RECIST 1.1 as assessed by the investigator) is defined as the time from the date of randomization until the date of documented response. The date of documented response should coincide with that used for the RECIST 1.1 DoR endpoint.

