The assessment of progression of  $\geq 20\%$  increase in the sum diameters of target lesions compared with the nadir is at the first progression time point relative to the nadir (the smallest sum of diameters and this may be at baseline or subsequent follow-up visit). The confirmed scan confirms the persistence of the  $\geq 20\%$  increase relative to the nadir.

- And/or clinically significant progression (worsening) of non-target lesions (NTL) or new lesions at the confirmatory PD time point compared with the first time point where progression of non-target lesions or new lesions identified
- And/or additional new unequivocal lesions at the confirmatory PD time point compared with the first time point new lesions were identified.

RECIST 1.1 will be regarded as primary in terms of the efficacy analyses and RECIST 1.1 modified for confirmation of progression assessment is supportive (Section 3.1.3).

In the absence of significant clinical deterioration, the investigator should continue study treatment until progression is confirmed.

If progression is not confirmed, then the patient should continue on study treatment and on treatment assessments. Treatment through PD in the Standard of Care group is at the Investigator's discretion; however, a confirmatory scan is required for all patients in the Standard of Care group, if clinically feasible, even if a subsequent treatment is started.

If a patient discontinues treatment (and/or receives a subsequent cancer therapy) prior to progression, then the patient should still continue to be followed until confirmed objective disease progression.

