## 3.2 Outcome Variables

All RECIST assessments, whether scheduled or unscheduled, will be included in the calculations. This is also regardless of whether a patient discontinues investigational product or receives another anti-cancer therapy. All efficacy and PRO data will be summarized and analysed using the full analysis set (FAS), refer to Table 6 for the analysis set for these variables.

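### ORR excludes responses first seen after a subsequent anticancer therapy but BoR does not, so CR + PR in the BoR table need not equal the ORR numerator

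*SAP*

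**What the plan says.** **ORR.** SAP 3.2.2 counts patients with at least one CR or PR visit up to progression, or up to the last evaluable assessment if there is none. It then adds an exclusion: "Patients who discontinue study treatment without progression, receive a subsequent therapy, and then respond will not be included as responders in the ORR". Protocol 8.4.1.3 has the same rule: "Patients who go off treatment without progression, receive a subsequent therapy, and then respond will not be included as responders in the ORR".

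**BoR.** SAP 3.2.11 uses the same window but has no such exclusion: "BoR will be determined programmatically based on RECIST 1.1 using all site investigator assessments up until the first progression event". Protocol 8.4.1.3 agrees: "BoR will be determined programmatically based on RECIST 1.1 using all investigator assessments up until the first progression event". For a best response of CR or PR, the SAP asks only that it be seen before PD. For SD it asks for a recording at least 35 days after randomization.

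**Default for tumour assessments.** SAP 3.2 brings all RECIST assessments into the calculations and adds: "This is also regardless of whether a patient discontinues investigational product or receives another anti-cancer therapy". SAP 3.1.2 and Protocol 8.4.1.2 say the same of investigator assessments.

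**Follow-up.** Scanning does not stop at a change of therapy. SAP 3.1 says: "If a patient discontinues treatment (and/or receives a subsequent cancer therapy) prior to progression, then the patient should still continue to be followed". Protocol 5.1 and Appendix E agree.

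**DoR and TTR.** SAP 3.2.3 starts DoR at "the latest of the dates contributing towards the first visit response of CR or PR" and leaves it undefined only where no response is documented. SAP 3.2.4 ties TTR to the DoR response date. The analysis sections (SAP 4.2.5 and 4.2.6; Protocol 8.5.2.3 and 8.5.2.5) speak of responding patients and of responders, and define neither.

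**Tumour size.** SAP 3.2.10: "Best percentage change from baseline in tumor size will also be derived as the biggest decrease". No cut at subsequent therapy is given. SAP 4.2.11 plots the result against a line at -30%, which it associates with partial response.

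**The concern.** ORR and BoR are both secondary endpoints in the PD-L1 TC/IC high subgroup and in all-comers, both by investigator RECIST 1.1. A reader of the study report will expect CR + PR in the BoR table to match the ORR numerator, and DoR and TTR to describe those same patients. As the rules stand, a response that first appears on a later therapy is kept out of ORR but credited to the randomised arm in BoR. It may also enter DoR and TTR, depending on how the programmer reads an undefined term. Neither document gives a reason for treating the endpoints differently. The trial is open-label, so the choice should be written down before the data are analysed.

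**Working it through.** No sample size, power or alpha figure depends on this point, so there is no planned number to reproduce. The check compares the rules and follows one patient through them.

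**Can the exclusion be read into BoR?** ORR and BoR have the same assessment window. ORR needs a separate sentence to remove responses seen after a switch, so the window alone does not remove them. BoR has no such sentence, and the default in SAP 3.2 points towards inclusion. A programmer following the text would include them.

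**Can the case arise?** Yes. Patients who stop treatment or start a new therapy before progression are still scanned until confirmed progression. Palliative radiation is outside the case, because SAP 4.1 does not count it as subsequent therapy. Responses after progression are already outside both ORR and BoR.

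**Hypothetical patient (course assumed).** SD at weeks 6 and 12; stops for toxicity without progression; starts a new systemic therapy at week 14; first PR, at -35%, at week 18; PD at week 40.

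| Output | Rule | As written | With the cut applied |
|---|---|---|---|
| ORR | SAP 3.2.2 | Non-responder | Non-responder |
| BoR | SAP 3.2.11 | PR | SD |
| DoR | SAP 3.2.3 | Week 18 to week 40, unless responders are taken to mean ORR responders | Not defined |
| TTR | SAP 3.2.4 | Week 18, with the same proviso | Not defined |
| Best change | SAP 3.2.10 | -35%, past the -30% line | From weeks 6 and 12 only |

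**A gap the cut would open.** Suppose a patient switches before the first scan and then shows PR. Once that PR is barred, no SD has been recorded before the switch either, so the rule must say which category applies.

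**Size per patient.** Let k be the number of patients in an arm whose first CR or PR follows a subsequent therapy started without progression. This rule difference alone gives:

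(CR + PR in BoR) - (ORR numerator) = k, which is k/n of the arm.

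For k = 1:
- all-comers, monotherapy or SoC (n = 190): 1/190 = 0.53%, or 0.5 percentage points;
- PD-L1 TC/IC high, monotherapy or SoC (n = 86, SAP Table 5): 1/86 = 1.16%, or 1.2 percentage points.

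k itself needs the proportion switching before progression and the response rate after switching. The documents give neither.

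**The case against.** The strongest reply is that little depends on this. BoR has no formal analysis, DoR has no comparison or p-value, TTR is descriptive and tumour size is shown in plots. ORR, the only response endpoint with a treatment comparison, already has the exclusion. Formal testing is for OS alone. All of that stands and limits the weight of the point, but it does not remove the contradiction between two tables of named secondary endpoints.

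A second reply is that inclusion is the SAP's default and ORR the exception, so it is not self-evident which rule should govern. That is fair. A single definition of responder used throughout would also reconcile the tables. The ORR rule is the natural one to extend because both documents state it explicitly. The safety summaries also apply a cut at first subsequent therapy, so that events reflect study treatment (SAP 4.2.13.1).

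Three stronger readings are tempting, and the documents do not support them:
- **That DoR and TTR plainly contradict ORR.** A reader might infer this from the derivation sections alone. The analysis sections restrict both to responders, and the ORR section is where the plan says who does not count as one. Reading them as ORR responders is reasonable. The fault there is an undefined term.
- **That the waterfall plot makes the patient a responder.** It classifies no one. It can show an ORR non-responder with a bar past -30%, on a supportive plot.
- **That SoC, or the arm with more toxicity, is favoured.** A reader might infer this because antibodies against PD-1 or PD-L1 are barred only during study treatment (Protocol 7.7). No rates of stopping or switching by arm are given, and in SoC a single drug can be dropped for toxicity while the others continue (Protocol 1.2.4 and 7.2.1).

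**Conclusion.** The conflict between ORR and BoR is real, appears in both documents, and is not resolved elsewhere in them. The same patient can be an ORR non-responder and a CR or PR for BoR. For DoR and TTR the finding is narrower: the exclusion is missing from the derivations and the population term is undefined, so the set described may differ from the ORR responders. For best percentage change it is a matter of presentation.

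The number affected cannot be calculated from the documents. Only the weight of one patient can be given: 0.5 percentage points among 190 or 1.2 among 86. The conclusion assumes only that at least one patient starts another therapy without progression and then responds for the first time. It concerns consistency of secondary and supportive outputs. The OS analysis and control of type I error are unaffected, and no bias towards any arm is shown. It should be corrected before analysis, chiefly because correction is easy.

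**What to change.** 1. In SAP 3.2.11 and Protocol 8.4.1.3, determine a BoR of CR or PR only from assessments up to the earlier of first progression and the start of the first subsequent anticancer therapy. Palliative radiation does not count as such a therapy, as in SAP 4.1.
2. In the same place, state that a patient with no qualifying CR, PR or SD before the switch is assigned PD or NE under the existing rules.
3. In SAP 3.2.3 and 3.2.4, and the matching protocol text, state that DoR and TTR are derived only for ORR responders. Use that term in SAP 4.2.5 and 4.2.6.
4. In SAP 3.2.10, apply the same cut to best percentage change, or flag post-switch values on the plot.
5. Leave the PFS rule and the end date of DoR unchanged.

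The cost is a few sentences in each document and one programming condition on the start date of first subsequent therapy, which TFST already requires (SAP 3.2.7). The reported BoR response may fall slightly. No trial procedure changes.
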